7.1.3. Sensitivity efficacy analyses

The following sensitivity analysis will be performed including the one defined in Section 7.1.1.

Objective: To repeat the primary analysis redefining the endpoint to exclude inconclusive tests with Ct>38 from the definition of the endpoint.

Outcome: Polymerase chain reaction (PCR)-confirmed SARS-CoV-2 infection (self-collected samples collected daily Day 1 through Day 14])

Cohorts: mITT Cohort

Definition of Endpoint: A participant will be defined as having the endpoint if at least one of their PCR tests throughout follow-up is positive (both targets are identified or the Ct is <=38) or they develop confirmed COVID-19 through external evaluation (e.g. hospital or clinical assessment).

Analysis Details:

The same analytical approaches will be applied as for the primary efficacy analysis with a positive test now being defined as concordant results (positive) or a Ct <=38. Inconclusive tests will be treated as negative.

7.1.4. Stratified Analyses

All efficacy analyses will also be repeated within subgroups defined by contact type, site, symptomatic index case, household size, time to start intervention, quarantine status, duration of exposure to index case (8 hours or less vs more than 8 hours) and presence of children in household. These subgroup analyses will only be adjusted for the same baseline covariates as the primary analysis (excluding the variable used to define the subgroup). For each of these subgroups, the cumulative incidence of the primary endpoint of SARS-CoV-2 infection by 14 days will be estimated, including 95% confidence intervals within each strata and a 95% confidence interval of the difference in cumulative incidence at 14 days between strata.

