11.3.1. Efficacy Analyses

Demographic characteristics (age, sex, race) of each study group will be tabulated.

The mean age (plus range and standard deviation) by sex of the enrolled participants, as a whole and per group, will be calculated.

The primary analysis will be performed using the modified Intention-to-Treat population. If the participant is not SARS-CoV-2 positive by laboratory test, their infection time will be censored at the last negative swab test date at or before the Day 14 swab. A logistic model stratified by site and accounting for within-household correlation will be used to assess the efficacy of the HCQ group compared to control. To aid understanding of the results from the logistic model, cumulative incidence Kaplan-Meier curves of time to infection will be presented by site and treatment arm.

Subgroup Analyses

All subgroup analyses will be pre-specified in the Statistical Analysis Plan. Any further subgroups will be considered *ad hoc*.

Missing Data

Due to the design of the study and retention activities, we expect to be able to categorize all infections as either incident or prevalent at baseline. However, in the unlikely event of a missing test result, the missing data will be imputed.

Additional analyses will be described in the Statistical Analysis Plan finalized before database lock.

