2.3. RANDOMIZATION

Enrolled contacts were randomized 1:1 to receive either HCQ or ascorbic acid. Randomization tables were stratified by study site and contact type (household/social exposure or healthcare worker exposure) and blocked into groups of randomly varying size. The tables were programmed in R and allocation was performed via REDCap by site pharmacists or their designees. All other study staff were blinded to randomization group apart from the coordinating center's unblinded statistical team.

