7.1.1. Primary efficacy analyses

Objective: To estimate the efficacy of HCQ (400 mg orally daily for 3 days then 200 mg orally daily for an additional 11 days, to complete 14 days) to prevent incident SARS-CoV-2 infection, compared to ascorbic acid among contacts of persons with SARS-CoV-2 infection.

Outcome: Polymerase chain reaction (PCR)-confirmed SARS-CoV-2 infection through Day 14

Cohorts: mITT Cohort, Sensitivity Cohort

Definition of Endpoint: An endpoint defining PCR test is defined as one with either concordant results or $Ct \leq 40$ and will be referred to as positive test for this analysis. PCR tests not meeting these criteria will be referred to as negative. A participant will be defined as having reached the endpoint on the midpoint between the days of collection of their first positive result and last negative result (prior to the positive result) in the first 13 days of follow-up. Participants who have confirmed COVID-19 through external evaluation in the first 13 days (e.g. hospital or clinical assessment) will be defined as having reached the endpoint at the midpoint between the last prior negative test and the day of the external diagnosis. Participants who do not reach the endpoint will have their follow-up censored at their last negative RNA test. Any uncertainty in final endpoint determination will be resolved by the blinded Endpoint Adjudication Committee.

Analysis Details:

The primary analysis will be performed on the mITT Cohort. A sensitivity analysis will be performed on the Sensitivity Cohort to account for potential missed infections at day 1.

We will use a Cox Proportional Hazards model with robust standard errors to estimate the hazard ratio and corresponding 95% confidence interval and Wald test statistic. Efficacy will be calculated as 1 minus the hazard ratio (treatment/control) from the treatment coefficient. Robust confidence intervals and p-values will be displayed. Per FDA guidance on prevention studies, the following variables will be included to increase precision: quarantine status, sex, and age of contact.

The number of evaluable participants per arm will be displayed (defined as participants with at least one PCR test result or external diagnosis) by arm with person-days of follow-up and number of endpoints per arm and prevalence of endpoints (number reached endpoint/number evaluable) with a 95% confidence interval calculated using exact binomial confidence intervals.

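### SAP 7.1.4 compares 14-day infection risk between strata without naming an arm, and plans no comparison of the subgroup hazard ratios with each other

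*SAP*

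**What the plan says.** Protocol 11.3.1 leaves the matter to the SAP: "All subgroup analyses will be pre-specified in the Statistical Analysis Plan". SAP 7.1.4 then specifies two things.

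- **Treatment effects inside subgroups.** "All efficacy analyses will also be repeated within subgroups defined by contact type, site, symptomatic index case, household size" and four more factors: delay before starting study drug, quarantine status, length of exposure to the index case, and children in the household. That makes eight. Under SAP 7.1.1 each repeat is a Cox model in which "Efficacy will be calculated as 1 minus the hazard ratio (treatment/control) from the treatment coefficient", with robust confidence intervals and p-values displayed. The covariates are those of the primary model, less the one that defines the subgroup.
- **Cumulative incidence.** For each subgroup, "the cumulative incidence of the primary endpoint of SARS-CoV-2 infection by 14 days will be estimated, including 95% confidence intervals within each strata", followed by "a 95% confidence interval of the difference in cumulative incidence at 14 days between strata". Neither clause mentions a study arm, and the section does not define strata.

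Neither document mentions a treatment-by-subgroup term, a test of heterogeneity or a ratio of HRs.

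**The concern.** The usual purpose of a subgroup section is to ask whether the treatment effect differs between kinds of participant. A difference in cumulative incidence between, say, household and healthcare contacts shows which group is infected more often. It can be large when HCQ works equally well in both groups, and zero when HCQ works in one and not in the other.

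The within-subgroup HRs do address efficacy, but the plan provides no way to compare them. Readers would be left to set one subgroup's p-value beside another's. With 93 events, it is common by chance alone for one subgroup to be significant and the other not. What is at stake is the interpretation of the subgroup results for eight factors.

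**Working it through.** **Inputs.** From SAP 2.4: 93 events, 1240 baseline-negative participants, 10% control risk, 50% reduction, 90% power, one-sided 0.025. From SAP 2.3: 1:1 allocation. From SAP 4: two-sided 0.05 for tests in general. Stratum risks and event splits are not in the documents; those below are assumptions.

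**1. The plan's own figures.** SAP 7.1.4 gives no number, so the design figures set the information available. With the bounds of SAP Table 1 at 19, 37, 56, 74 and 93 events and HR 0.5, power is 90.3% and one-sided alpha 0.0251. With looks at every fifth of the total, 92 events give just under 90%. Participants: 93 / ((0.10 + 0.05)/2) = 1240. Both figures reproduce.

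**2. What the literal contrast measures.** Take two equal strata of 620, with 310 per arm. The incidence in a stratum, with no arm distinguished, is the mean of its two arm risks. The variance of the difference is p1(1-p1)/620 + p2(1-p2)/620.

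| | Stratum 1, control/HCQ | Stratum 2, control/HCQ | Risk ratios | Between-strata difference (95% CI) |
|---|---|---|---|---|
| A: same efficacy | 14% / 7% | 6% / 3% | 0.5 and 0.5 | 10.5 - 4.5 = 6.0 points (3.1 to 8.9) |
| B: reversed efficacy | 10% / 5% | 5% / 10% | 0.5 and 2.0 | 7.5 - 7.5 = 0.0 points (-2.9 to 2.9) |

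Both cases have 93 events: A has 310 x 0.21 + 310 x 0.09 = 65.1 + 27.9, and B has 46.5 + 46.5. In case A the interval excludes zero although the ratio of risk ratios is 1.0. In case B it centres on zero although that ratio is 0.5/2.0 = 0.25 (95% CI 0.11 to 0.58, z = -3.26). Milder cases behave the same way. Risks of 10%/5% against 7.5%/7.5% give a difference of 0 with risk ratios 0.5 and 1.0. Risks of 12%/6% against 6%/3% give 4.5 points with equal risk ratios.

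**3. What separate models show when efficacy is uniform.** Let the true HR be 0.5 everywhere, with independent outcomes and SE(log HR) = 2/sqrt(events).

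- Even split, 46.5 events each: SE = 0.293 and power = Phi(0.693/0.293 - 1.96) = 66%. The chance that exactly one of the two levels reaches p < 0.05 is 2 x 0.66 x 0.34 = 45%.
- 80:20 split, 74.4 and 18.6 events: powers are about 85% and 32%, and the chance of exactly one is 62%.

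**4. What a direct comparison would offer.** SE(log ratio of HRs) = sqrt(4/e1 + 4/e2).

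- Even split: sqrt(8/46.5) = 0.415, and exp(1.96 x 0.415) = 2.25. Power for a ratio of 2 is 39%; 80% power needs a ratio of about 3.2.
- Even split at the design HR of 0.5: information per event is 0.5/1.5^2 = 2/9 instead of 1/4, so SE = sqrt(2/(46.5 x 2/9)) = 0.44 and the CI factor is 2.37.
- 80:20 split: SE 0.518, CI factor 2.76, and 27% power for a ratio of 2.

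Household correlation would widen these intervals.

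**5. Multiplicity.** Eight independent tests at 0.05: 1 - 0.95^8 = 34% chance of at least one false positive.

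**The case against.** **Arms are compared in every subgroup.** A reader might infer that the between-strata difference is the only formal comparison in the section, or that no subgroup treatment effect is estimated. The text does not support that: the first sentence of SAP 7.1.4 yields an HR, robust CI and p-value in each subgroup. What is missing is narrower, namely a comparison of those HRs with each other.

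**Strata may mean arms.** It would also go too far to say that the SAP pools the arms; it does not say so. If a subgroup is a single level, the strata inside it could be the arms, and the contrast would then be a within-subgroup risk difference. Protocol 11.3.1 lends some support by planning Kaplan-Meier cumulative incidence by site and treatment arm, and SAP 5.2 stratifies adherence by arm. Against this, SAP 7.1.4 never mentions arm, and SAP 2.3, 4 and 7.1 use stratification for site or contact type. The risk-factor reading is the more literal one, and the calculations in step 2 of the working depend on it. The absence of a heterogeneity comparison does not.

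**Imprecision is visible.** Each subgroup HR carries its CI (a factor of about 1.8 either way at 46.5 events), and for a two-level factor a reader could approximate the ratio of HRs. This stands. It would be wrong to say that the plan conceals the uncertainty; only the uncertainty of the comparison goes unreported.

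**Interaction tests have little power, and eight of them invite false positives.** Both are true. They are reasons to present the ratio as an exploratory estimate with its interval. They do not favour leaving readers to compare p-values, given step 3. It is also true that the SAP has no objective on effect modification, which limits the weight of the point.

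**Conclusion.** The point holds in this form. Read literally, the only cross-subgroup comparison in SAP 7.1.4 measures differences in infection risk and can mislead in both directions about differences in efficacy. If arms were intended, the wording does not say so. On either reading nothing compares the subgroup HRs.

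The 6.0-point and 0.0-point examples rest on assumed stratum risks; the logic does not depend on the particular values. The CI factor of about 2.25 to 2.4 for the ratio of HRs assumes 93 events split evenly, 1:1 allocation and independent outcomes. Uneven splits or household correlation make it wider.

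The consequence is confined to subgroup interpretation. The primary analysis, sample size and interim monitoring are unaffected.

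**What to change.** In SAP 7.1.4:

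- **(a)** Replace the between-strata difference with 14-day cumulative incidence by arm within each subgroup level, and the HCQ-minus-control difference with its 95% CI. Differences on this scale can vary between levels when relative efficacy is constant (case A: -7 and -3 points), so they do not stand in for (b).
- **(b)** For each factor, add a treatment-by-subgroup term to the primary Cox model, together with the factor's main effect where it is not already a covariate or a baseline-hazard stratum. Report the ratio of HRs with its robust 95% CI. For factors with more than two levels, use a joint test. Set cut-points in advance for household size and time to start, for which the section gives none.
- **(c)** Label these analyses exploratory. State that power is low and that about a 34% chance of at least one false positive would arise over eight independent tests, and emphasise the estimate and CI over the p-value.

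The cost is a few sentences of SAP text and one extra model per factor, with no new data. The downside is wide intervals that will rarely settle whether efficacy differs.

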8. INTERIM ANALYSIS AND DATA MONITORING COMMITTEE

[figure not shown]
8.1. EFFICACY AND FUTILITY MONITORING

Interim monitoring will be performed on the primary outcome after approximately 20%, 40%, 60% and 80% of expected events. Monitoring will be performed using asymmetric O'Brien-Fleming bounds for early stopping for efficacy (lower) and futility (upper). The Wald test statistic from the robust Cox model without adjustment for covariates will be using for monitoring the trial with fraction of planned households as the information fraction[1].

Table 1 Monitoring bounds with 4 interim analyses. Expected events may vary and actual stopping bound will be based on number of events observed at the time of monitoring.

Analysis	Expected number of events	Efficacy bound	Futility bound (binding)
1	19	-4.50	2.7
2	37	-3.18	0.64
3	56	-2.60	-0.52

4	74	-2.25	-1.35
5	93	-2.01	-2.01

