11.1. Sample Size Determination

Not all individuals exposed to COVID-19 will become infected, and early estimates place family members at a 3% to 15% risk of infection after likely exposure [32, 33]. The sample size required to show a 50% protective efficacy of PEP is entirely dependent on that attack rate. Sample size calculations used an estimated 6% attack rate.

A sample size will be chosen for each group (HCQ and ascorbic acid) to achieve 80% power with 0.05 two-sided Type 1 error for the endpoint of any laboratory-detected incident SARS-CoV-2, exclusion of participants with positive SARS-CoV-2 at baseline, an attack rate of 6%, 50% efficacy of HCQ in reducing SARS-CoV-2 incidence, and randomizing the first household member enrolled and subsequent household members to the same intervention. With these assumptions, a cohort of 1498 households (749 in the control and 749 in the intervention for each cohort) will provide at least 80% power to detect a decrease in SARS-CoV-2 incidence from 6% to 3%. As household size increases, power will increase.

Household members will be randomized as a unit but analyzed as individuals.

The table below estimates power assuming that households are randomized until either 1498 households are randomized or 1498 individuals are randomized. Each row shows the distribution of the numbers of individuals within a household who are randomized. Individual risk is assumed to be independent. Power may be lower depending on correlation in risk within and between households (Table 1).

Table 1 Power to Detect a Decrease from 6% to 3% Under Hypothetical Distributions of Number of Household Contacts

Number in Household	Distribution of Number Randomized Within Household					Number of Households is the Target			Number of Participants is the Target		
	1	2	3	4	5	N _{HH}	N _p	Power	N _{HH}	N _p	Power
A	0.8	0.1	0.06	0.03	0.01	1498	2022	89%	1108	1498	78%
B	0.75	0.15	0.06	0.03	0.01	1498	2097	90%	1070	1498	78%
C	0.25	0.35	0.16	0.13	0.11	1498	3745	99%	600	1498	76%

N_{HH}: number of households; N_p: number of participants.

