2.4. SAMPLE SIZE AND POWER

Since finalization of the protocol and at the recommendation of the DSMB, the study size has been recalculated as an event-driven design. The original study was designed under 80% power with a target number of households, assuming 1 infection per household, recognizing there would

likely be more than 1 per household and therefore power would be at least 80%. In the spirit of accounting for the within household correlation without any existing estimates of what it may be, we instead assume 90% power with 50% reduction and 4 interim analyses (for 5 total) and a one-sided alpha = 0.025 and a hard futility boundary. Under these design assumptions, the design requires 93 events. Assuming a household attack rate of 10% in the placebo arm (higher than in protocol and based on emerging evidence (UM study and HH study from China that looked at masks and disinfecting), we would need to enroll 1240 participants who are negative at baseline.

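### SAP 8.1 gives two clocks for the stopping bounds: the text uses households, while the look schedule, Table 1 and its caption use events

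*SAP*

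**What the plan says.** SAP 2.4 reports that, on the DSMB's recommendation, "the study size has been recalculated as an event-driven design". It assumes 90% power for a 50% reduction, one-sided alpha 0.025, five analyses and a hard futility boundary, and concludes: "Under these design assumptions, the design requires 93 events". With a 10% control attack rate this becomes 1240 baseline-negative participants. No planned number of households is given. The only household target in either document is the 1498 in Protocol 11.1, which belongs to the design that SAP 2.4 replaced.

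SAP 8.1 then says three things about the monitoring clock:

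- Look schedule: "Interim monitoring will be performed on the primary outcome after approximately 20%, 40%, 60% and 80% of expected events".
- Information fraction: the unadjusted robust Cox Wald statistic is monitored "with fraction of planned households as the information fraction[1".
- Table 1 caption: "Expected events may vary and actual stopping bound will be based on number of events observed at the time of monitoring".

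Table 1 lists expected events of 19, 37, 56, 74 and 93. It has no household column, and its futility column is labelled binding.

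**The concern.** Timing looks by events while measuring information on another scale is not in itself a contradiction. The caption makes it one, because it ties the bound actually applied to observed events while the text ties it to households. Two different bounds can then apply at the same look.

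The household rule has two further gaps. Its denominator is not in the SAP. Its numerator is also undefined, since the text does not say whether a household counts when enrolled, when followed up or at some other point.

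Nor is a count of households the natural information measure for a log hazard ratio. That information accrues with events and, under household randomization, depends on the robust variance.

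Because futility is binding, the DSMB could be obliged to stop under one reading and to continue under the other.

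**Working it through.** **Inputs.** From SAP 2.4: 93 events, 50% reduction (taken as HR 0.5), one-sided alpha 0.025, five analyses, binding futility, 10% control attack rate, 1240 participants. From SAP 2.3: 1:1 allocation. From SAP 8.1: the Table 1 bounds. From Protocol 11.1: attack rates of 6% and 3% to 15%.

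**Step 1: reproduce the plan.** With information fraction t = 0.2, 0.4, 0.6, 0.8, 1.0:

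- Efficacy bound = −c/√t
- Futility bound = −2c√t + c/√t

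Solving for one-sided alpha 0.025 with futility obeyed gives c = 2.013. The bounds are:

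| Look | Events | Efficacy | Futility |
|---|---|---|---|
| 1 | 19 | −4.50 | 2.70 |
| 2 | 37 | −3.18 | 0.64 |
| 3 | 56 | −2.60 | −0.52 |
| 4 | 74 | −2.25 | −1.35 |
| 5 | 93 | −2.01 | −2.01 |

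This is Table 1. The number of events for 90% power is 92.2, rounded up to 93. The participant number also reproduces: pooled risk 0.10 × 0.75 = 0.075, and 93/0.075 = 1240. At 93 events the drift is ln(0.5) × √(93/4) = −3.342 and power is 90.3%. So Table 1 fits an event clock and needs no new numbers.

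**Step 2: how far the bounds can differ at one look.** At 56 events Table 1 gives −2.60 and −0.52. A household fraction of 0.50 would give −2.85 and 0.00; 0.70 would give −2.41 and −0.96; 0.80 would give −2.25 and −1.35.

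**Step 3: effect on the whole trial.** Looks are kept at 20/40/60/80/100% of events. The covariance of the statistic follows events, the bounds are read at the household fraction, and futility is obeyed (c = 2.01). The household fractions are assumptions, because the documents fix none. Power and the futility stop are at HR 0.5.

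| Household % at the five looks | Power | Interim futility stop | One-sided alpha |
|---|---|---|---|
| 20/40/60/80/100 (equal to events) | 90.3% | 5.5% | 0.025 |
| 10/30/50/70/100 | 91.0% | 2.2% | 0.0240 |
| 25/45/65/85/100 | 89.2% | 8.0% | 0.0255 |
| 30/50/70/90/100 | 87.4% | 11.1% | 0.0255 |
| 40/60/80/95/100 | 82.6% | 16.9% | 0.0255 |
| 50/70/85/95/100 | 76.9% | 22.8% | 0.0253 |

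**Step 4: the documents' own attack rates at look 2 (37 events).** This assumes 50% efficacy, constant contacts per household, no follow-up lag, and 1240 participants standing in for the missing household target. Participants at the look = 37/(0.75 × control rate); fraction = participants/1240. The mean of Z at HR 0.5 is −3.342 × √(37/93) = −2.108.

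- SAP rate ("Assuming a household attack rate of 10% in the placebo arm"): 37/0.075 = 493, fraction 0.40. The bound is Table 1's 0.64, with a futility-stop chance at that look of 0.3%.
- Protocol rate ("Sample size calculations used an estimated 6% attack rate"): 37/0.045 = 822, fraction 0.66. The futility bound is −0.81, with a futility-stop chance of 9.6%.
- Top of the Protocol range ("early estimates place family members at a 3% to 15% risk of infection after likely exposure"): 37/0.1125 = 329, fraction 0.27. The futility bound is 1.83, and the efficacy bound is −3.90 instead of −3.18.

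These are single-look illustrations. With the denominator held at 1240, a 6% rate yields only 1240 × 0.045 = 56 events, so the fraction reaches 1.00 at look 3. At a 15% rate it is only 93/0.1125/1240 = 0.67 when 93 events are reached.

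**The case against.** **The intended reading is recoverable.** Everything around the phrase points to events: the event-driven sizing, the look schedule, the table and the caption. On that reading the bounds work as designed and nothing is lost. This stands as a reason for moderate severity. It does not remove the contradiction, since a binding rule should not depend on the DSMB choosing which of two sentences to ignore.

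**The scenarios are assumed.** No household lead is documented. A 5-point lead costs only about one point of power (89.2%), and a lag slightly raises it. The 6% attack rate was superseded by 10%, at which the two clocks coincide under the stand-in, and Protocol 11.1 and Appendix 2 let the enrolment target be revised. All of this stands, so 76.9% is not an expected value. Still, if enrolled households are what is counted, a lead is the likelier direction. Endpoints accrue over 14 days after enrolment, swabs may be collected in batches (Protocol 9.1.2), and testing is not in real time (Protocol 9.1.5). That the fixed-denominator fraction reaches 1 too early at 6% also shows how poorly such a clock tracks the design.

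**Households may have been chosen to reflect clustering.** This is possible. With a robust variance and unknown within-household correlation, events/93 is itself only approximate information, and the power figures above treat it as exact. The caption would still conflict with the text and the denominator would still be missing.

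**Other sources may settle it.** The Interim Monitoring Plan named in Protocol 11.1 and the reference attached to the phrase were not available. A household target may be stated there, so the statement that the rule cannot be computed applies to the SAP text only.

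**Conclusion.** The concern holds. SAP 8.1 defines the monitoring clock in two incompatible ways, and only the event clock matches Table 1 and SAP 2.4. If the caption governs, the design has its stated properties. If the household phrase governs, power at HR 0.5 ranges from 91.0% with a 10-point lag to 76.9% with the largest lead examined, and interim futility stopping from 2.2% to 22.8%. These figures rest on assumed household fractions, on events as the true information, and on futility being obeyed. One-sided alpha stays between 0.024 and 0.0255, so type I inflation is not the issue. This should be fixed because it can change a binding stopping decision.

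**What to change.** In SAP 8.1, remove the household definition. State once that the information fraction is the number of observed primary-endpoint events in the mITT Cohort divided by 93. Make the Table 1 caption say the same, and state that both bounds are recomputed from that fraction at each look and that the final analysis is at 93 events.

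If the team wants the clock to reflect household clustering, observed robust-variance information over its planned maximum is an alternative. The SAP would then have to state that maximum, which it does not do now, and the caption would have to be rewritten to match.

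The cost is one sentence plus agreement with the caption, with no extra participants or data. The edit belongs before the first interim look. If a look has already taken place, the clock used should be documented. If the Interim Monitoring Plan repeats the household phrase, it needs the same edit.
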